5.2.2 Secondary Endpoints

- The percentage of subjects with physician's clinical global assessment on Day 3 of treatment.
- The percentage of subjects with subject's rating of medication helpfulness impression on Day 7 and 14 of treatment.
- The percentage of subjects with physician's clinical global assessment on Day 7 and 15 of treatment.
- The percentage of subjects with subject-rated global impression (relief from local pain, restriction in activities of daily living, restriction of movement, intensity of local pain) of on Day 3, 7 and 14 of treatment.
- The percentage of subjects defined as responders on Day 3, 7 and 14 of treatment.
- The percentage of subjects with physician rated assessment of presence of muscle spasm, presence of local pain, limitation of range of motion, limitation of activities of daily living on Day 3, 7 and 15.

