9.1.6 Primary Efficacy Measurement

The measures of effectiveness in this study will include:

- **Subject's rating of medication helpfulness:**

Subjects will be asked to assess it on a daily basis (in the daily diary), using the following 5-point rating scale: "How would you rate this study medication in improving your condition?"

"0 = poor"

"1 = fair"

"2 = good"

"3 = very good"

"4 = excellent"

Assessment of the subject's answers will be made for the Day 3, 7 and 15.

- **Physician's clinical global assessment :**

The investigator will be asked to assess their clinical global impression of change compared to Baseline, based on physical examination, degree of muscle spasm (presence of muscle spasm assessment), reaction to palpation (presence of local pain assessment), limitation of range of motion, and evaluation of the patient's reported functional assessment (limitation of activities of daily living assessment). The following 5-point rating scale will be used:

"1 = worse"

"2 = no change"

"3 = slight improvement"

"4 = moderate improvement"

"5 = marked improvement"

Assessment will be made for the Day 3, 7 and 15.

- **The subject-rated relief from local pain:**

Subjects will be asked to assess on a daily basis (in the daily diary) their level of relief from local pain due to the muscle spasm (in either the lower back or cervical spine) compared to Baseline (Visit 1) using the following 5-point rating scale:

"1 = no relief"

"2 = a little relief"

"3 = some relief"

"4 = a lot of relief"

"5 = complete relief"

Assessment of the subject's answers will be made for the Day 3, 7 and 15.

- **The subject-rated restriction in activities of daily living:**

Subjects will be asked to assess on a daily basis (in the daily diary) the change in the severity of restriction in the activities of daily living compared to Baseline (Visit 1) using the following 5-point rating scale:

"1 = worsening"

"2 = no change"

"3 = mild improvement:"

"4 = moderate improvement"

"5 = marked improvement"

Assessment of the subject's answers will be made for the Day 3, 7 and 15.

CONFIDENTIAL

- **The subject-rated restriction of movement:**

Subjects will be asked to assess on a daily basis (in the daily diary), the change in restriction of movement due to the muscle spasm compared to Baseline (Visit 1) using the following 5-point rating scale:

“1 = no relief”

“2 = a little relief”

“3 = some relief”

“4 = a lot of relief”

[figure not shown]
“5 = complete relief”

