Assessment of the subject’s answers will be made for the Day 3, 7 and 15.

- **The subject-rated intensity of local pain:**

Subjects will be asked to assess on a daily basis (in the daily diary) their intensity of local pain due to the muscle spasm (in either the lower back or cervical spine) using the following digital rating scale. It is necessary to mark the intensity of pain by circling a one of the 11 points from 0 "No Pain" to 10 "Severe Pain" with an intermediate value of 5 - "Moderate Pain".

Facial pain scale is presented to help the patient to identify the primary area of the intensity of the pain experienced:

Assessment of the subject’s answers will be made for the Day 3, 7 and 15.

- **Subject-Rated Clinical Global Impression:**

[figure not shown]
Subjects will be asked to assess on a daily basis (in the daily diary) their clinical global impression of change compared to Baseline, based on rating on medication helpfulness, relief from local pain, restriction in activities of daily living, restriction of movement.

Assessment of the subject’s answers will be made for the Day 3, 7 and 15.

Company Confidential Information

Company Confidential Information

Company Confidential Information

- Hematology, blood chemistry, urinalysis, urine pregnancy testing (if applicable), vital signs, physical examinations, and ECGs will be performed at Screening and study termination. Vital signs will be recorded at each clinic visit. Monitoring and recording of AEs will be performed during each clinic visit and continued for 3 weeks after the last dose of study drug.

Other assessments:

- **Presence of muscle spasm**

The physician was asked to evaluate the presence of muscle spasm by palpation (increased consistency of a muscle or group of muscles) using the following 5-point rating scale at each visit:

“1 = none” (no muscle spasm present)

“2 = mild” (the muscle is somewhat harder than usual)

“3 = moderate” (muscles are hard and borders of increased consistency can be determined by palpation)

“4 = moderately severe” (muscles are very hard and borders are sharply defined by palpation)

“5 = severe” (board-like hardness of the muscles)

- **Presence of local pain**

The physician was asked to assess the presence of local pain due to muscle spasm by palpation (tenderness on palpation) using the following 5-point rating scale at each visit:

“1 = none” (no pain)

“2 = mild” (complaint of local discomfort on palpation)

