“3 = moderate” (objective evidence that the area is painful, such as defensive movements, reflex dilatation of pupils, etc.)

“4 = moderately severe” (the area is very painful)

“5 = severe” (the area is intolerably painful and subject objects to the examination)

CONFIDENTIAL

- **Limitation of range of motion**

The physician was asked to assess at each visit, the subject's limitation of range of motion using the following 5-point rating scale:

"1 = none" (no limitation in range of motion)

"2 = mild" (restriction of the normal motion by 10-15%)

"3 = moderate" (restriction of the motion by no more than 50%)

"4 = moderately severe" (restriction of the expected motion by no more than 80%)

"5 = severe" (the subject has great difficulty in attempting to perform one or more of the major motions)

- **Limitation of activities of daily living**

The physician was asked to assess by both direct observation and historical questioning, the limitation of activities of daily living using the following 5-point rating scale at each visit:

"1 = none" (no limitation of activities of daily living)

"2 = mild" (the subject is able to perform his customary tasks, but with discomfort)

"3 = moderate" (the subject is able to perform partially with discomfort some essential tasks and activities)

"4 = moderately severe" (the subject performs partially with great difficulty some essential tasks and activities)

"5 = severe" (the subject is unable to perform most of the essential tasks or activities)

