9.3.2 Randomization

Randomization will take place on Day1 (could be the same day at which Screening visit took place). The following procedures will be performed and documented during Randomization:

- Vital Signs (if not same day as Screening procedures).
- Concomitant medications.
- Adverse Events.
- The following parameters will be assessed by the investigator: presence of muscle spasm, presence of local pain, limitation of activities of daily living, and limitation of range of motion.
- Subject Diary dispense. Subjects should be instructed :
 - To complete assessment for Day 1 at the hospital before the first drug intake.
 - Starting from Day 2 record the following assessments (compared to Baseline) in the daily diary: rating of medication helpfulness, relief from local pain, subject-rated Clinical global impression, restriction in activities of daily living, and restriction of movement;
 - To record the following assessments in the daily diary: **Company Confidential Information** intensity of local pain **Company Confidential Information** ;
 - To complete their diary during 14 days at the same time each day if possible but record the worst feeling/symptom since the diary was last completed. No diary to be completed at Day 15 (Visit 4) but returned to the Investigator.
 - To bring their diary to each study visit for review by Investigator. Completed pages will be collected by Investigator, then the diary will be dispensed to subject again.
- If the subject has satisfied all of the inclusion criteria and none of the exclusion criteria for randomization, the subject should be randomized using the IVRS/IWRS, as described in Section 8.2.
- Study drug dispense. The medication identification (ID) number of the study drug will be provided via IVRS/IWRS. To avoid any overdose and non-compliance with study drug intake, original bottle containing 60 capsules with CER 15 mg or Placebo will be opened in front of the subject and 40 capsules of 60 will be removed in cleanliness condition and put into the additional bottle for keeping at the site (never dispensed to subject) until destruction. Original bottle containing 20 capsules with CER 15 mg or Placebo will be dispensed to subject. Subject will be instructed to:
 - To swallow one capsule whole with 180 mL of room temperature water, once daily in the evening between 18:00 and 19:00 starting from Day1.

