Hard gelatin capsules with blue to blue-green body with white imprint “1002-30” and red to red-orange cap with white imprint “EUR”. Capsule content - white to yellow spherical granules.

Pharmacotherapeutic group: Central muscle relaxant

ATC code: M03BX08

Pharmacological properties

Pharmacodynamics

Cyclobenzaprine cures skeletal muscle spasm not affecting muscle function. Animal studies showed that cyclobenzaprine does not directly affect neuromuscular transmission or directly skeletal muscles. Cyclobenzaprine reduced or eliminated skeletal muscle hypertension on animal models. Data of the studies also showed that cyclobenzaprine primarily affects central nervous system at cerebral trunk level. Inhibition of neuromuscular transmission at the level of spinal cord also plays role in general myorelaxing effect on skeletal muscles. Data available indicate that direct effect of cyclobenzaprine is reduction of tonic somatic motor activity by affecting both gamma (γ)- and alpha (α)-motor systems. Pharmacological studies on animals demonstrated similar effect of cyclobenzaprine and structurally related tricyclic antidepressants, including antagonism in relation to reserpine, potentiation of noradrenaline, express peripheral and central anticholinergic effect and sedation. Cyclobenzaprine induced slight to moderate increase of heart rate in animal studies.

Pharmacokinetics

Absorption

After single administration of cyclobenzaprine in a dose of 15 mg and 30 mg by healthy volunteers (n = 15), dose-dependent increase of C_{max} , AUC_{0-168h} and AUC_{0-∞} has been observed. Maximum cyclobenzaprine concentration in blood plasma is reached in 7 - 8 hours for both dosages.

Cyclobenzaprine pharmacokinetics does not depend on food ingestion. C_{max} value increases to 35%, AUC increases to 20%, however first concentrations of cyclobenzaprine in blood plasma are observed in 1.5 hour, with or without food.

In multiple dose study with administration of 30 mg of cyclobenzaprine once a day within 7 days in a group of healthy volunteers (n = 35) with steady state concentration, 2.5 fold increase of cyclobenzaprine concentration in blood plasma has been observed.

Metabolism and excretion

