As long as no controlled studies of cyclobenzaprine use in pregnant women have been performed, it should not be taken during pregnancy.

Lactation

Stop breastfeeding during treatment with cyclobenzaprine, as far as no data of drug permeability to breast milk are available.

Posology and administration

Per os, without chewing, washing down with a small amount of water.

1 capsule of Myorix® in a dose of 15 mg once a day. Some patients might need dose increase up to 30 mg/day. In this case, take 1 capsule of Myorix® in a dose of 30 mg once a day, or 2 capsules of Myorix® in a dose of 15 mg once a day.

It is recommended to take the drug at the same time of a day. Treatment course duration - not more than 2 - 3 weeks.

Adverse reaction

Incidence of side effects of the drug is evaluated as follows:

Very often: $\geq 1/10$,

Often: $>1/100$, $<1/10$;

Not often: $>1/1000$, $<1/100$;

Seldom: $\geq 1/10\ 000$, $< 1/1000$,
Very seldom: $< 1/10\ 000$.

General disorders:

Not often: faintness, sickliness, chest pain, edemas;

Cardiovascular system disorders:

Not often: tachycardia, fibrillation, vasodilation, rapid heartbeat, arterial hypotension/hypertension, myocardial infarction, myocardial conduction defect, stroke;

Disorders of gastrointestinal tract:

Very often: dry mouth;

Often: constipation, nausea, dyspepsia, bad taste;

Not often: vomiting, anorexia, diarrhea, abdominal pain, gastritis, thirst perception, bloat, paraglossa, liver dysfunction;

Seldom: hepatitis, jaundice, cholestasis, paralytic ileus, discoloration of tongue, stomatitis, parotiditis;

Endocrine system disorders:

Not often: syndrome of inappropriate antidiuretic hormone;

Disorders of blood and lymphatic system:

Not often: purpura (hemorrhagic rash), myelosuppression, leukopenia, eosinophilia, thrombocytopenia;

Immune system disorders:

Not often: hypersensitivity response in the form of anaphylactic edema or angioedema, itching, facial edema, urticaria, rash;

Metabolism and nutritional disorders:

Not often: high or low blood glucose level, increased or reduced body weight;

Musculoskeletal system disorders:

Not often: local muscle weakness, myalgia;

Nervous system and mental disorders:

Often: drowsiness, dizziness, increased fatigability, asthenia, blurred vision, headache, nervousness, confused consciousness;

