neuromuscular transmission (e.g., tremor, ataxia, hyperreflexia, myoclonus, rigid muscles), gastrointestinal disorders (e.g., nausea, vomiting, diarrhea). In case the above reactions take place, immediately stop treatment with Myorix® and any associated serotonergic medicinal product and start symptomatic treatment. If associated treatment with Myorix® and other serotonergic medicinal products is clinically reasonable, it is recommended to provide thorough monitoring, especially during the beginning of therapy or dose increase.

Effects, similar to effects of tricyclic antidepressants.

Cyclobenzaprine has similar structure with tricyclic antidepressants (amitriptyline, imipramine). There are registered reports that tricyclic antidepressants cause heart rhythm disorder, sinus tachycardia, increased conduction time based on cardiac conduction system, which may lead to myocardial infarction or stroke (ref. to *Contraindications* Section).

Some of more serious reactions of CNS, observed in tricyclic antidepressants, were observed also in studies of cyclobenzaprine use for other indications and usually in doses far exceeding doses recommended for use in case of skeletal muscle spasms. In case of clinically significant symptoms of effect on CNS, consider possibility to withdraw treatment with Myorix®.

Elderly patients

It is not recommended to use Myorix® in elderly patients due to increase of cyclobenzaprine content in plasma to 40 % and increase of elimination half-time to 56 % after administration of the drug by elderly patients compared to younger patients.

Patients with liver function abnormality

It is not recommended to use Myorix® in patients with slight, moderate or severe liver dysfunction due to double increase of cyclobenzaprine content in plasma in patients with slight liver dysfunction compared to patients without liver dysfunction due to limited possibility of drug dose change.

Atropine-like action

Prescribe Myorix® with care to patients with data on urinary retention, angle-closure glaucoma, elevated intraocular pressure in medical history, and in patients taking anticholinergic drugs due to atropine-like action of cyclobenzaprine.

Effects on ability to drive and use machines

Pursuant to adverse reactions profile, it is recommended to abstain from activity, requiring high alertness and promptness of psychomotor reaction, e.g., driving vehicles or working with machines and mechanisms.

Presentation

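### Grade 3 of the physician's local-pain scale names pupil dilatation as a sign of pain, which an atropine-like study drug may confound in the CER arm only

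*Protocol*

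**What the plan says.** In Section 9.1.6, under the other assessments, the physician is to "assess the presence of local pain due to muscle spasm by palpation (tenderness on palpation") on five grades at each visit. Grade 2 (mild) rests on the subject complaining of discomfort when palpated. Grade 3 (moderate) rests on "objective evidence that the area is painful, such as defensive movements, reflex dilatation of pupils, etc". Grades 1, 4 and 5 do not mention the pupil.

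The rating is used in two places:

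- It is a secondary endpoint in Section 5.2.2: "The percentage of subjects with physician rated assessment of presence of muscle spasm, presence of local pain", with two further physician ratings, at Days 3, 7 and 15. Section 13.1.3 plans frequency counts and percentages for it and no test.
- It is an input to the physician's clinical global assessment, which Section 9.1.6 bases among other things on "reaction to palpation (presence of local pain assessment"). Section 13.1.3 analyses that assessment at Days 3, 7 and 15 in the same way as the primary endpoint, that is, with a two-sample Wilcoxon rank sum test.

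Appendix E describes the drug's pharmacology from animal studies as including "express peripheral and central anticholinergic effect and sedation". Its special precautions call for care in patients with a history of angle-closure glaucoma or raised intraocular pressure, and "in patients taking anticholinergic drugs due to atropine-like action of cyclobenzaprine".

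**The concern.** An observer's rating compares two arms fairly only if the sign being graded means the same thing in both. Pupil size is under autonomic control, and the protocol's own leaflet calls the study drug atropine-like. If CER changes the pupil or its reactivity, a rater who uses this example is partly grading the drug. Placebo subjects have no such source of error, so it would not cancel between arms.

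What is at stake is the description of one secondary endpoint and, less directly, one component of another secondary endpoint that is tested. Section 6.2 relies on blinded raters to keep the assessment objective. Blinding does not remove an error of this kind, because the sign itself may differ by arm.

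**Working it through.** The protocol gives no figure that depends on this anchor, so there is nothing to reproduce. The check sets the passages side by side and then shows how any misgrading would translate into the summary table.

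**1. Where the sign sits.** Mild needs only a complaint; moderate needs objective evidence. The pupil is one of two named examples in an open list, and it acts at the boundary between grades 2 and 3.

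**2. Could the drug plausibly interfere?** Appendix E states the atropine-like action. It lists dry mouth as very often (at least 1 in 10) and, among the reactions it rates as often (more than 1 in 100, less than 1 in 10), blurred vision: "Often: drowsiness, dizziness, increased fatigability, asthenia, blurred vision, headache, nervousness, confused consciousness". Both fit peripheral anticholinergic action. The list covers the 15 mg and 30 mg capsules without separating them. Dilated pupils are not listed, so a pupil effect at 15 mg is an inference and not a documented fact.

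**3. Is drug present when the scale is rated?** Section 9.3.2 schedules one capsule each evening from Day 1 to Day 14. Appendix E gives a peak at 7 to 8 hours and a half-life of 32 hours. Drug would be present at the Day 3, Day 7 and Day 15 ratings.

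**4. Does the baseline rating help?** At randomization, "The following parameters will be assessed by the investigator: presence of muscle spasm, presence of local pain" and two other items, on Day 1, when the first capsule is due that evening. That rating is free of drug effect. Interference could therefore appear only after baseline and only in the CER arm, so neither randomization nor a comparison with baseline removes it.

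**5. Which direction?** There are two routes:

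- A drug-related wide pupil is taken as evidence of pain. Some true grade 1 or 2 subjects become grade 3, and CER looks worse.
- An already wide or less reactive pupil hides the reflex. Some true grade 3 subjects with no other sign become grade 2, and CER looks better.

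The documents do not say which would dominate.

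**6. Illustration, on assumed values only.** Suppose there is no true treatment difference. Let s be the share of CER subjects whose true grade is 1 or 2, and f the fraction of them raised to grade 3 by the pupil sign. The CER-minus-placebo shift in the percentage graded 3 or higher is then s × f.

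| s | f = 0 | f = 0.05 | f = 0.10 | f = 0.20 |
|---|---|---|---|---|
| 0.3 | 0 | +1.5 points | +3 points | +6 points |
| 0.5 | 0 | +2.5 points | +5 points | +10 points |
| 0.7 | 0 | +3.5 points | +7 points | +14 points |

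With 90 subjects per arm, 2.5 points is 0.025 × 90 = 2.25 subjects and 5 points is 0.05 × 90 = 4.5 subjects. Masking gives a shift of the opposite sign: minus the share of CER subjects truly at grade 3, times the fraction whose grade rested on the pupil alone. Neither s nor f can be estimated from the documents, and f = 0 is possible.

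**7. How far it travels.** The table applies to the descriptive summary of local pain. The tested variable, the physician's global assessment, is an impression of change that also draws on physical examination, spasm, range of motion and daily activities. Any effect there would be diluted by an amount the documents do not let us calculate. The primary endpoint is the subject's own rating of helpfulness and makes no use of the pupil.

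**The case against.** The strongest reply is that the anchor describes a reflex provoked by palpation, not resting pupil size. A careful rater can tell a pupil that widens on pressure from one that is wide throughout, and defensive movement alone is enough for grade 3. Much of this stands, and it limits the likely error. It does not remove it: a pupil that is already wide or sluggish makes the reflex harder to read, and the protocol gives raters no instruction on the matter. A separate rater guide, not at hand, might.

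The protocol also intends its measurement methods to resemble those of the earlier pivotal studies (Section 6.2). That is a fair reason for keeping the anchor, but resemblance does not require identical wording.

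A reader might infer more than the documents support:

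- **That the grade is distorted in the CER arm.** No passage reports a pupil effect at 15 mg. The adverse reaction and overdose lists in Appendix E do not name one, and the anticholinergic statement comes from animal work.
- **That the bias runs against CER.** The masking route is just as open.
- **That a planned test of local pain loses power.** No such test is planned, so there is no power to lose.
- **That raters are directed to look at the pupils, which undermines the blind.** The pupil is an optional example. Dry mouth and drowsiness are listed as common reactions, and adverse events are asked about at the same visits, so any extra unblinding through the pupil is speculative.

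**Conclusion.** The point holds as a possible differential measurement error in one anchor of one secondary rating. Its size is unknown and its direction undetermined. It rests on one inference: that a drug the protocol calls atropine-like and anticholinergic may affect the pupil at the study dose. If it does not, the anchor does no harm.

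The consequences are bounded. The local-pain scale is only summarized, the tested global assessment is reached indirectly and in diluted form, and the primary analysis is untouched. Severity is minor. It is worth raising because the sign adds little to the scale and the risk can be removed by editing a few words.

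**What to change.** In Section 9.1.6, delete the pupil example from the grade 3 anchor and keep defensive movements as the named sign of objective evidence. Add one sentence to the rater instructions saying that pupil size is not part of the pain grade, since the list of signs is open-ended and a rater might otherwise still count it. Make the same change on the rating form.

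The cost is a few words in the protocol and the form, and a slight departure from the wording of the earlier studies. Nothing in dosing, visits, sample size or analysis changes.
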